## **Study Protocol and Statistical Analysis Plan with Results**

A total of 69 patients with uncontrolled open-angle glaucoma were recruited at the George Washington University by two glaucoma attending professors. Research protocol approval was obtained from the institutional review board of George Washington University (Washington, DC, USA) under IRB #041, 310 and registered on ClinicalTrials.gov with identifier NCT01956942. Written informed consent was received from all patients, and the protocol followed the Declaration of Helsinki.

This study included all laser trabeculoplasty candidates with open-angle glaucoma on maximally tolerated medical therapy with the need for additional IOP lowering. Patients with end-stage, neovascular, uveitic, or angle closure glaucoma were excluded. In all, 38 patients were randomized to MLT and 31 patients to SLT via a random number generator protocol approved for up to 100 patients. All patients had only one eye included in the study. Patients were allocated to each group without any stratification based on prior characteristics via sealed numbers in a set sequence. Recruitment was concluded after a power analysis revealed an 80% power at a 0.05  $\alpha$  level detecting an average 2.99 mmHg or 16.19% decrease from baseline between the SLT and MLT groups. This level was determined based on prior studies defining a \$3 mmHg or \$20.0% decrease in IOP as a significant difference from baseline.11 Patients, physicians, and researchers were not blinded to the different laser treatments. Each of the two physicians performed both the laser treatments and all subsequent follow-ups for a particular patient.

The MLT group underwent 360° treatment with the IQ 577 nm™ yellow laser (Iridex Corporation, Mountain View, CA, USA) with laser applied to the pigmented trabecular meshwork in a confluent manner. The laser settings for MLT were 1,000 mW, 300 ms duration, 300 µm spot size, and a 15% duty cycle. The SLT group received 360° treatment with the 532 nm Q-switched, frequencydoubled Nd:YAG Selecta II™ (Lumenis Inc, San Jose, CA, USA). The energy for SLT was titrated, between ~0.6 and ~2.0 mJ, based on trabecular meshwork pigmentation to achieve a noticeable gas bubble response, utilizing a 400 µm spot size and a 3 ns duration.

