All patients were treated with one drop of apraclonidine prior to the treatment. Patients were discharged with topical diclofenac 0.1% to use as needed for discomfort. At week 1, patients completed a standardized survey querying discomfort experienced both during and after the procedure and use of the topical diclofenac.

Patients' IOP was measured at predefined intervals of 1 hour and 1-, 6-, 6–12-, 12–24-, 24–36-, and 36–52-week intervals based on a fixed follow-up of 1 and 6 weeks and a tendency to follow these patients every 3–4 months thereafter. Pretreatment IOP values were calculated as the average of up to three preceding visits to reduce fluctuations. Only the preceding visits without the addition of a drop or a laser were included to avoid confounding influences. If patients were examined multiple times within an interval, IOP values were averaged for statistical analysis. Patients' responses were excluded from the analysis if they underwent any interventions that may affect their IOP, including the addition of a topical antihypertensive drop, cataract surgery, cyclophotocoagulation, incisional glaucoma surgery, or further laser trabeculoplasty. However, their data were still included for the intervals up to the time of these interventions. Comparison between groups was calculated with Student's *t*-test for continuous data and a two-tailed Fisher's exact test for categorical data.

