## Results

There was no statistically significant difference in demographic characteristics between groups, as seen in Table 1. The MLT patients had a higher average starting IOP (18.26 mmHg) than the SLT group (16.85 mmHg), approaching significance (P=0.08). Both groups had very similar 1 hour posttreatment IOP, 15.15 mmHg in the MLT group and 15.65 mmHg in the SLT group. An IOP spike was defined as an elevation of .5 mmHg from the pretreatment mean. Incidence of post-procedure spikes were 5.3% and 12.9% in the MLT and SLT groups, respectively, but this difference was not statistically significant (P=0.4). No group experienced any anterior chamber inflammation upon examination at the 1 week follow-up time point.

Follow-up data at the 1-, 1–6-, 6–12-, 12–24-, 24–36-, and 36–52-week intervals were tabulated as absolute IOP decreases from pretreatment levels (Figure 1) and percentage IOP decreases from baseline (Figure 2). These data demonstrated that both MLT and SLT provided comparable decreases in IOP from baseline as both an absolute measurement and a percentage decrease at all intervals up 52 weeks (*P*.0.05). In addition, the confidence intervals at each time period were, 3 mmHg when viewed as an absolute decrease in IOP and, 20.0% when viewed as a percentage decrease from baseline IOP, except one outlier interval (week 24–36 in Figure 1). A Kaplan–Meier curve is demonstrated in Figure 3. As expected, the larger proportion of failures in the MLT group produced a lower curve, with more of the MLT failures occurring in the early period. However, the survival curve steps in both groups were similar at later intervals, leading to a log-rank *P*-value of 0.31.

The data from the standardized pain survey (scale of 0= none to 10= severe) revealed that the MLT patients experienced a mean 1.34/10 during treatment and 0.89/10 during the 1 week posttreatment period, while the SLT patients noted 2.83/10 during treatment and 2.81/10 during the 1 week posttreatment period. The MLT patients on average experienced less pain both during and after the treatment (P=0.005).

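### One-hour IOP is called similar on raw means alone, without a test or baseline adjustment, although the arms started 1.41 mmHg apart

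*Combined protocol and SAP*

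**What the plan says.** The methods text (section *Study Protocol and Statistical Analysis Plan with Results*) puts 1 hour first in its measurement schedule: "Patients' IOP was measured at predefined intervals of 1 hour and 1-, 6-, 6–12-, 12–24-, 24–36-, and 36–52-week intervals". Baseline is defined there too: "Pretreatment IOP values were calculated as the average of up to three preceding visits to reduce fluctuations". Continuous outcomes are to be compared with Student's t-test; no baseline adjustment is named.

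The *Results* section reports the starting pressures: "The MLT patients had a higher average starting IOP (18.26 mmHg) than the SLT group (16.85 mmHg), approaching significance (P=0.08". The next sentence gives the 1-hour outcome: "Both groups had very similar 1 hour posttreatment IOP, 15.15 mmHg in the MLT group and 15.65 mmHg in the SLT group". No SD, CI or P value goes with it. The spike rates follow, 5.3% for MLT and 12.9% for SLT (P=0.4), with a spike defined as a rise above the pretreatment mean.

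The later times are handled on another scale: "Follow-up data at the 1-, 1–6-, 6–12-, 12–24-, 24–36-, and 36–52-week intervals were tabulated as absolute IOP decreases from pretreatment levels", and also as percentage decreases. One hour is not in that list. The conclusion from the listed intervals is that "both MLT and SLT provided comparable decreases in IOP from baseline as both an absolute measurement and a percentage decrease at all intervals".

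**The concern.** The power statement, the tabulated comparison, the spike definition and the success criteria all work relative to baseline. The 1-hour mean is the exception, and no reason is given. The choice of scale matters because the arms did not start level. If the arm that starts higher ends at about the same pressure, its mean fall was larger.

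At stake is the reading of the only acute post-laser mean in the document. A reader who takes the sentence at face value will conclude that the two lasers had the same early effect on pressure. That has not been tested. The one formal acute comparison, on spikes, rests on 2 and 4 events and has little power, so a continuous comparison at 1 hour would be more informative.

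**Working it through.** **Inputs.** Pretreatment means 18.26 (MLT) and 16.85 (SLT), P=0.08; 1-hour means 15.15 and 15.65; spike rates 5.3% and 12.9%, P=0.4 (all from *Results*). Arm sizes: "38 patients were randomized to MLT and 31 patients to SLT" (methods text). The SD of change, the slope of 1-hour IOP on baseline and the 1-hour denominators are not given. They are assumed below, with all 38 and 31 patients taken to supply both means.

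**Step 1. Reproduce a stated figure.** 5.3% of 38 is 2 patients and 12.9% of 31 is 4. A two-tailed Fisher's exact test on 2/38 against 4/31 gives P=0.397, which matches the printed 0.4.

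**Step 2. Put 1 hour on the scale used for the weekly intervals.**
- MLT: 18.26 − 15.15 = 3.11 mmHg (3.11/18.26 = 17.0%)
- SLT: 16.85 − 15.65 = 1.20 mmHg (1.20/16.85 = 7.1%)
- Difference in fall: 3.11 − 1.20 = 1.91 mmHg, larger in MLT

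**Step 3. Split the 1.91.** Baseline gap: 18.26 − 16.85 = 1.41. Raw 1-hour gap: 15.65 − 15.15 = 0.50. The sum is 1.91, and 1.41/1.91 = 74% of it is baseline imbalance.

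**Step 4. Adjust for baseline.** With a common slope *b* of 1-hour IOP on pretreatment IOP, the adjusted difference is 0.50 + *b* × 1.41.

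| Assumed *b* | Adjusted difference (mmHg) |
|---|---|
| 0 (raw comparison) | 0.50 |
| 0.3 | 0.92 |
| 0.5 | 1.21 |
| 0.7 | 1.49 |
| 1 (change score) | 1.91 |

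The raw contrast is right only if baseline pressure tells us nothing about pressure at 1 hour in the same eye. The unadjusted change score is right only if *b* = 1. For slopes between 0 and 1 the answer lies between the two.

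**Step 5. Precision of the unadjusted difference.** SE = SD × √(1/38 + 1/31) = SD × 0.242, with 67 degrees of freedom.

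| Assumed SD of change (mmHg) | SE | t | P | 95% CI (mmHg) |
|---|---|---|---|---|
| 3 | 0.73 | 2.63 | 0.011 | 0.46 to 3.36 |
| 4 | 0.97 | 1.97 | 0.053 | −0.02 to 3.84 |
| 4.41 | 1.07 | 1.79 | 0.078 | −0.22 to 4.04 |
| 5 | 1.21 | 1.58 | 0.12 | −0.51 to 4.33 |

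The 4.41 is the SD implied by the power statement: 2.99/[(1.96 + 0.84) × 0.242], within rounding. P is below 0.05 only if the SD is below about 3.95.

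**Step 6. Precision of an adjusted difference, for illustration.** The baseline P=0.08 corresponds to t = 1.78, which implies a baseline SD of 1.41/(1.78 × 0.242) ≈ 3.28. Assume that SD at both times and a correlation of 0.5, so *b* = 0.5. The residual SD is 3.28 × √(1 − 0.25) = 2.84. Allowing for the baseline gap, SE = 2.84 × √[1/38 + 1/31 + 1.41²/(67 × 3.28²)] ≈ 0.70. The adjusted difference of 1.21 then has P of about 0.09 and a 95% CI of about −0.2 to 2.6 mmHg.

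**The case against.** The strongest reply is that the sentence is literally true and nothing is concealed. It speaks of posttreatment IOP, and the raw means are 0.50 mmHg apart. Both baseline means stand in the sentence before, so any reader can derive the 1.91. That stands: the fault is an analysis not reported, not a result hidden.

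Four further replies also limit the point.
- A reader might infer that the statement of comparable decreases at all intervals is false because 1 hour was left out. The documents do not support this. The statement refers back to the listed intervals, which begin at week 1.
- A reader might infer that 1 hour is the one time at which the arms differ. The text prints no weekly means, and Figures 1 and 2 are not available here, so this cannot be judged.
- The acute period is not ignored. Spikes are measured against the pretreatment mean, reported by arm and tested.
- The 1.91 mmHg is mostly baseline imbalance, lies below the 2.99 mmHg used in the power statement, and would tend to overstate a laser effect through regression to the mean.

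Regression to the mean does not rescue the raw comparison, however. Any positive slope moves the adjusted difference above 0.50, and averaging up to three visits for baseline reduces the noise that would weaken the slope. Apraclonidine was given to every patient, so by itself it does not explain a gap between arms.

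**Conclusion.** The point holds as a reporting and analysis gap of modest size. A preset time point is described as similar on raw means, untested, and on a different scale from the weekly intervals. The raw 0.50 mmHg understates the between-arm difference if baseline IOP positively predicts 1-hour IOP. A plausible adjusted figure is 0.9 to 1.5 mmHg in the direction of a larger fall with MLT, resting on an assumed slope of 0.3 to 0.7 and on the same patients supplying both means.

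A tempting stronger reading is that the arms have been shown to differ at 1 hour. They have not. The SD of change is missing, and P for the unadjusted difference runs from about 0.01 to 0.12 over assumed SDs of 3 to 5 mmHg. Under the Step 6 assumptions the adjusted interval includes zero and stays inside 3 mmHg. The direction agrees with the lower spike rate in MLT, but that comparison is not significant either. The omission is judged from the text's list of intervals, since the figures cannot be seen. The conclusions on IOP decrease to 52 weeks, success at 24–52 weeks and failure do not use the 1-hour mean.

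**What to change.** - Analyse 1-hour IOP by ANCOVA with pretreatment IOP as covariate, and report the between-arm difference with a 95% CI. An unadjusted change score should not be the main estimate.
- Show absolute and percentage change at 1 hour descriptively, with SDs and the number of patients measured in each arm.
- Replace the similarity wording with that result, read beside the spike rates (5.3% against 12.9%, P=0.4).
- State that the conclusion of comparable decreases covers week 1 to week 52 only.

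The cost is one more comparison on data already collected and a few changed sentences. The downside is that the similarity statement may become less favourable.

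### Post-procedure IOP spikes are measured against the mean of earlier visits, with no laser-day pre-drop reading described, so spike status partly reflects visit-to-visit change

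*Combined protocol and SAP*

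**What the plan says.** The spike definition is in Results: "An IOP spike was defined as an elevation of .5 mmHg from the pretreatment mean". The threshold sign appears to have been lost when the text was extracted, as in other inequalities in the same section, and I read it as more than 5 mmHg.

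The methods text defines the reference: "Pretreatment IOP values were calculated as the average of up to three preceding visits to reduce fluctuations". It adds: "Only the preceding visits without the addition of a drop or a laser were included to avoid confounding influences".

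Premedication was the same in both arms: "All patients were treated with one drop of apraclonidine prior to the treatment".

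The schedule reads: "Patients' IOP was measured at predefined intervals of 1 hour and 1-, 6-, 6–12-, 12–24-, 24–36-, and 36–52-week intervals". The 1-hour reading is thus the only scheduled one before week 1. The spike sentence itself gives no time point, but it directly follows the 1-hour results. No laser-day reading before the drop and the laser is described anywhere.

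The result is: "Incidence of post-procedure spikes were 5.3% and 12.9% in the MLT and SLT groups, respectively", with P=0.4.

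**The concern.** Averaging earlier visits suits efficacy, where the aim is a stable baseline. A spike is a different quantity: an acute rise attributed to a procedure on one day. Measured against a historical mean, the recorded change has three parts: the laser effect, the drop effect, and the gap between that day's starting pressure and the past mean. The third part has nothing to do with the laser.

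A patient who arrives 5 mmHg above the historical mean is at the threshold before treatment. One who arrives 4 mmHg below it can rise 8 mmHg and be recorded as only 4 mmHg up. Averaging steadies the reference but leaves the laser-day fluctuation in full. Because the mean uses up to three visits, some references may be a single reading.

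A transient pressure rise is the only complication the document reports, so this definition carries the acute safety comparison.

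**Working it through.** **Inputs from the document.** 38 MLT and 31 SLT patients; spikes 5.3% and 12.9%; pretreatment means 18.26 and 16.85 mmHg; 1-hour means 15.15 and 15.65 mmHg; two-tailed Fisher's exact test.

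**Assumed, because not given.** Visit-to-visit SD *s* of 2 to 3 mmHg; normal, independent fluctuation; threshold of more than 5 mmHg; spike judged at 1 hour.

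**1. Reported P.** 2/38 = 5.3% and 4/31 = 12.9%. Two-sided Fisher on 2/38 v 4/31 gives P = 0.397, which matches the stated 0.4.

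**2. Mean 1-hour change from the historical reference.**
- MLT: 15.15 − 18.26 = −3.11 mmHg.
- SLT: 15.65 − 16.85 = −1.20 mmHg.
- Gap between arms: 3.11 − 1.20 = 1.91 mmHg. Of this, 18.26 − 16.85 = 1.41 comes from the reference (1.41/1.91 = 74%) and 15.65 − 15.15 = 0.50 from the 1-hour readings.
- At the arm means, a spike needs more than 23.26 mmHg in MLT and more than 21.85 mmHg in SLT.

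**3. Spikes from fluctuation alone.** The SD of a same-day reading minus the mean of *k* earlier visits is *s*·√(1 + 1/*k*). With mean change *m*, P(spike) = 1 − Φ[(5 − *m*)/(*s*·√(1 + 1/*k*))]. For example, SLT with *s* = 3 and *k* = 1: SD = 4.24, z = 6.20/4.24 = 1.46, P = 7.2%.

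| Reference | *s* | SD | MLT (*m* = −3.11) | SLT (*m* = −1.20) |
|---|---|---|---|---|
| three visits | 2 | 2.31 | 0.02% | 0.4% |
| three visits | 3 | 3.46 | 1.0% | 3.7% |
| one visit | 2 | 2.83 | 0.2% | 1.4% |
| one visit | 3 | 4.24 | 2.8% | 7.2% |
| reported | | | 5.3% | 12.9% |

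Setting *m* = 0 gives 1.5% to 7.4% (three visits) and 3.9% to 11.9% (one visit), but that ignores the observed falls.

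**4. Effect of the reference when responses also vary.** Keep the same mean changes, add a same-day response SD of 2 to 4 mmHg, take a visit-to-visit SD of 1.5 to 3 mmHg, and assume that a same-day reading cancels the visit-to-visit part. Expected spike rates are:

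| Reference | MLT | SLT |
|---|---|---|
| same day | 0.0–2.1% | 0.1–6.1% |
| mean of three visits | 0.1–6.3% | 1.0–12.1% |
| one earlier visit | 0.3–8.2% | 1.7–14.4% |

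The historical reference raises the expected rates in both arms. By how much depends on the assumptions.

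**5. Sensitivity of the comparison to reclassification.**
- One patient: 1/38 v 4/31 gives P = 0.166; 2/38 v 5/31 gives 0.230; 2/38 v 3/31 gives 0.651; 3/38 v 4/31 gives 0.69.
- Two patients: only 0/38 v 4/31 falls below 0.05 (P = 0.036). The others include 1/38 v 5/31 at 0.083, 2/38 v 6/31 at 0.127, and 4/38 v 4/31 at 1.0.

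**6. Precision.** Power to detect 5.3% v 12.9% with 38 and 31 patients is about 21%. About 221 per arm would be needed for 80%.

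**The case against.** The strongest reply is that both arms used the same reference rule under randomisation and averaging reduces noise on the reference side, so the rule adds noise and no expected bias. This stands. The 1.41 mmHg imbalance is a feature of this sample (P=0.08). It tilts the comparison only so far as it reflects past fluctuation. If MLT eyes were also higher on the laser day, a same-day reference would be higher too.

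A reader might infer that apraclonidine biases the comparison. The documents do not support that: every patient in both arms received it. It lowers absolute rates and can mask rises, but by itself it does not favour either laser unless the drop acts differently by arm, which nothing in the text suggests.

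A reader might also infer that fluctuation could account for the reported rates. That needs the assumption of no net effect of laser plus drop, which the observed falls contradict. With those falls, every figure in step 3 is below the reported rate in its arm.

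Finally, spikes are a secondary safety description. With six events the comparison is uninformative under either reference, and no efficacy, failure or pain result depends on this definition. This also stands and limits the weight of the point. It does not make the reference suitable for an acute event.

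**Conclusion.** The point holds as a measurement weakness. The rule as written classifies an acute event partly on visit-to-visit change. Fluctuation alone would produce about 0.02% to 2.8% spikes in MLT and 0.4% to 7.2% in SLT, given an assumed SD of 2 to 3 mmHg, a 5 mmHg threshold, the observed mean changes, and references of one to three visits. The 1-hour timing is a strong inference from the schedule and is not stated in the definition.

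It would be tempting to say that one or two misclassified patients would overturn the safety message in either direction. They would not: no single reclassification brings P below 0.166, only one two-patient change crosses 0.05, and none gives a significant result against MLT. Nor can the documents show that the counts of 2 and 4 would change under a same-day reference, since they give neither that reading nor a within-patient SD.

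**What to change.** **In the plan, or any further trial.** Record study-eye IOP on the laser day before apraclonidine. Define a spike as a rise above the stated threshold from that reading, at a stated time point (1 hour). Keep the averaged pretreatment IOP for efficacy only.

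**For the completed data.** State when spikes were assessed and whether a laser-day pre-drop reading exists. Where one is in the chart, re-classify spikes against it and report the result beside the present one. Otherwise state the limitation. In either case, label the rates as observed under apraclonidine premedication.

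**Cost.** One routine tonometry reading at a visit that already takes place, a one-line change to the definition, and a chart check for the completed data. A single-reading reference carries its own measurement error, and the reported percentages may change.

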Prior authors defined a successful laser trabeculoplasty as \$3 mmHg IOP decrease or \$20.0% IOP decrease from baseline.6,8 Using these criteria, 29.6% of the MLT and 36.0% of the SLT patients experienced a 20.0% IOP decrease from baseline during the 24–52-week interval (P=0.77). Similarly, 37.0% of the MLT patients and 36.0% of the SLT patients experienced a \$3 mmHg IOP reduction from baseline at the 24–52-week interval (P=1.0).

Patients in each group were also assessed to determine the proportion that required further intervention for their glaucoma during the 52-week follow-up period, indicating a failure of the laser therapy. In the MLT group, a total of 23.7% of patients failed and required further treatment for their glaucoma. A topical antiglaucoma agent was added in 15.8% of the MLT patients, incisional glaucoma surgery was performed in 2.6% of the MLT patients, and transscleral cyclophotocoagulation was performed in 5.3% of the MLT patients. In the SLT group, 12.9% of the patients failed, with all the failures due to the addition of another topical antiglaucoma medication. Although there were a greater number of failures in the MLT group (23.7%) compared to the SLT group (12.9%), the analysis did not meet significance in each individual category or when considered in sum (P=0.22). No patient in either group experienced any complications, other than a transient rise in IOP.

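### Inflammation is reported only from the week-1 examination, which cannot support an untimed statement of no complications where early, self-clearing inflammation is concerned

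*Combined protocol and SAP*

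**What the plan says.** The first paragraph of Results gives the only anterior chamber finding in the document: "No group experienced any anterior chamber inflammation upon examination at the 1 week follow-up time point". It gives no count of patients examined and no grading method.

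The last paragraph of Results ends with a general safety statement: "No patient in either group experienced any complications, other than a transient rise in IOP". It gives no period and no method of ascertainment.

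The contacts are described in the opening section (Study Protocol and Statistical Analysis Plan with Results): "Patients' IOP was measured at predefined intervals of 1 hour and 1-, 6-, 6–12-, 12–24-, 24–36-, and 36–52-week intervals". The schedule is said to be "based on a fixed follow-up of 1 and 6 weeks and a tendency to follow these patients every 3–4 months thereafter". At 1 hour, only IOP is described as measured. The same section states that "38 patients were randomized to MLT and 31 patients to SLT", and that categorical outcomes are compared with a two-tailed Fisher's exact test.

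Two further facts bear on how the week-1 result reads. "Patients were discharged with topical diclofenac 0.1% to use as needed for discomfort", so drops could be used before that examination. Also, "Patients, physicians, and researchers were not blinded to the different laser treatments", and the physician who gave the laser also did that patient's follow-up.

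**The concern.** A single look at week 1 measures inflammation present at week 1. It says nothing about inflammation that began after the laser and had gone by the time of that look. The general statement at the end of Results covers the whole period after treatment, so for this outcome it is wider than the examination reported in its support.

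What is at stake is a safety conclusion about two lasers. If early cases clear before week 1, the result is zero in both arms whatever the true incidence, and the arms look alike on inflammation because of when they were examined. A reader of the closing statement would take inflammation to have been excluded throughout.

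**Working it through.** **Inputs.** Randomised: 38 MLT and 31 SLT (opening section). Inflammation at week 1: none in either group (Results, first paragraph). Number examined at week 1: not stated. Categorical test: two-tailed Fisher's exact.

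**Step 1: reproduce the nearest safety figure in the document.** The inflammation zero has no calculation behind it, so the IOP spikes serve as a check on denominators and test. 2/38 = 5.3% and 4/31 = 12.9%, matching the stated percentages. Fisher's exact test gives P = 0.397, matching the stated 0.4. The spike result therefore uses the full randomised arms. This does not establish that all of them had an anterior chamber examination at week 1.

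**Step 2: what zero cases show about week 1.** The exact two-sided 95% upper limit for 0/n is 1 − 0.025^(1/n). If every randomised patient was examined:

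- MLT: 1 − 0.025^(1/38) = 1 − 0.9075 = 9.3%
- SLT: 1 − 0.025^(1/31) = 1 − 0.8878 = 11.2%
- Both arms together: 1 − 0.025^(1/69) = 5.2%

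Fewer patients examined would give higher limits. The 24–52-week success percentages fit 27 MLT patients (8/27 = 29.6%, 10/27 = 37.0%) and 25 SLT patients (9/25 = 36.0%). Later analyses therefore did not include everyone, and full attendance should not be taken for granted. If attendance at week 1 had been that low, the limits would be 1 − 0.025^(1/27) = 12.8% and 1 − 0.025^(1/25) = 13.7%.

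**Step 3: what zero cases show about any inflammation after laser.** Let p be the true incidence and s the share of cases still visible at week 1. The chance of seeing none is (1 − p·s)^n. With s = 0 this equals 1 for any p, so the zeros carry no information. For s above 0, the upper limit on p is the Step 2 limit divided by s. The documents give no value for s, so it is an assumption shown over a range, again with all 38 and 31 examined:

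| Assumed s | Upper limit, MLT | Upper limit, SLT |
|---|---|---|
| 1 | 9.3% | 11.2% |
| 0.5 | 18.5% | 22.4% |
| 0.25 | 37.0% | 44.9% |
| 0 | none | none |

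The zeros are informative if many cases last to week 1 and uninformative if none do. The documents do not say which applies.

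**Step 4: set the two statements side by side.** The first-paragraph sentence names its time point and claims nothing beyond it. The last-paragraph sentence names none. No examination reported in the document links the two for the days before week 1.

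**The case against.** The strongest reply is that the week-1 sentence is correct as written, and that the closing sentence is not a bare claim of no complications, because it excepts a transient rise in IOP. Both points stand. The document also draws no conclusion of equal safety from the inflammation zeros, and it compares spikes (5.3% v 12.9%, P=0.4) and pain (P=0.005) as further safety outcomes. The point is therefore confined to the missing time limit in the closing sentence, and to inflammation.

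A second reply is that the list of time points describes when IOP was measured and need not be a full list of examinations. The methods also allow for more than one examination within an interval. This stands too. A reader might infer that the anterior chamber was never looked at before week 1, but the documents are silent on that. All that can be said is that no earlier anterior chamber examination is reported.

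A reader might also infer that early inflammation did occur, or that it was commoner after SLT because mean pain in the first week was 2.81/10 with SLT against 0.89/10 with MLT. The documents do not support either. They give no time course for inflammation after laser and nothing that ties the pain scores to it. The scores come from patients who knew their treatment, and in the SLT arm pain during the procedure was almost the same (2.83/10).

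Finally, follow-up is complete, so new examinations cannot be added to this trial. That limits what can be changed now to reporting. It does not remove the mismatch between the closing statement and the examination behind it.

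**Conclusion.** The point holds in a limited form. Absence of inflammation is shown for week 1 among those examined. It is not shown for the period before week 1, so the untimed closing statement goes beyond the reported ascertainment for this one outcome. Other complications looked for during follow-up are not called into question, and the efficacy results and the spike and pain P-values are unaffected.

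The upper limits of 9.3% and 11.2% rest on the assumption that all randomised patients were examined at week 1, and they apply to week 1 only. For inflammation that clears earlier there is no limit. This conclusion needs no model of how long inflammation lasts, and it does not depend on whether anyone used diclofenac.

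**What to change.** 1. In the first paragraph of Results, report inflammation present at week 1 as 0/n per arm, with n the number actually examined, and exact 95% limits (upper limits 9.3% and 11.2% if n is 38 and 31). State that no earlier anterior chamber examination is reported, or give its result if one was done.
2. In the last paragraph of Results, limit the statement to say that, apart from temporary IOP elevation, no complication was recorded at the scheduled examinations.
3. In the plan, or any repeat of it, record anterior chamber cell and flare at the existing 1-hour contact and compare arms with the Fisher's exact test already specified. Acknowledge that the days between 1 hour and week 1 remain unexamined; the grading narrows the gap without closing it.

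Items 1 and 2 need only the week-1 examination counts and a change of wording. Item 3 needs a few minutes of grading at a contact that already takes place. The price is a slightly less favourable safety statement.

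### The Results say comparable IOP decreases were demonstrated at all intervals, but this rests on non-significant difference tests, and the confidence-interval statement supports at most a narrower claim

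*Combined protocol and SAP*

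**What the plan says.** The opening section, Study Protocol and Statistical Analysis Plan with Results, gives α = 0.05 and 80% power for "detecting an average 2.99 mmHg or 16.19% decrease from baseline between the SLT and MLT groups". It continues "This level was determined based on prior studies defining a" and gives the prior-study level as 3 mmHg or 20.0%, a change from baseline. The same section compares groups with Student's t-test (continuous data) and a two-tailed Fisher's exact test (categorical data), and lists weeks 24–36 among the predefined intervals. It contains no equivalence or non-inferiority hypothesis and no margin.

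The Results then conclude: "These data demonstrated that both MLT and SLT provided comparable decreases in IOP from baseline as both an absolute measurement and a percentage decrease" and apply this "at all intervals up 52 weeks", with P>0.05 in support. A second sentence adds that "the confidence intervals at each time period were" below 3 mmHg on the absolute scale and below "20.0% when viewed as a percentage decrease from baseline IOP", "except one outlier interval", identified as weeks 24–36 in Figure 1. The comparison signs in both sentences were lost in text extraction and are inferred here. Figures 1 and 2 are not shown.

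**The concern.** A t-test with P>0.05 says that the data are compatible with no difference. It does not say that differences of clinical interest have been ruled out. In a trial of 69 patients the two can be far apart, and only the interval for the between-laser difference tells the reader how far.

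The confidence-interval sentence could supply that information, but the text does not say what the intervals estimate. An interval for each arm's own fall in IOP would not measure the difference between lasers. An interval for the between-arm difference lying inside ±3 mmHg would exclude differences of 3 mmHg or more, and nothing smaller. The 3 mmHg/20.0% level enters as a change from baseline, and the Results later use it as a per-patient success criterion. Nowhere is it declared a tolerable difference between lasers.

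For week 24–36, the word outlier invites readers to discount an interval that was planned.

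At stake is the IOP conclusion. A reader may take comparability as established at every interval when moderate differences could easily have gone undetected.

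**Working it through.** **Inputs.** 38 MLT and 31 SLT patients; α = 0.05; 80% power at 2.99 mmHg (opening section). Baseline means 18.26 and 16.85 mmHg, P = 0.08; responders at weeks 24–52 of 29.6% and 37.0% (MLT) and 36.0% and 36.0% (SLT) (Results). No SD of IOP change is given, so it is an assumption and a range is used.

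**1. The stated power.** It cannot be reproduced without an SD, only solved backwards. With √(1/38 + 1/31) = 0.2420 and 67 degrees of freedom, a two-sided t-test has 80% power at 2.99 mmHg when SE = 1.052 mmHg, so SD = 1.052/0.2420 = 4.35 mmHg. This is the upper SD.

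**2. A lower SD.** The baseline difference is 18.26 − 16.85 = 1.41 mmHg. Two-sided P = 0.08 on 67 degrees of freedom is t = 1.778, so SE = 1.41/1.778 = 0.793 and SD = 0.793/0.2420 = 3.28, taken as 3.3 mmHg. This is an SD of baseline IOP, not of change, so it is only a second reference point.

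**3. Numbers at later visits.** The only denominator up to 38 that yields both 29.6% and 37.0% is 27 (8/27, 10/27). The only one up to 31 that yields 36.0% is 25 (9/25). Fisher's exact test then gives P = 0.77 and P = 1.0, as reported. So 27/25 is used as a later-interval case. The n at each separate interval is not in the text.

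**4. Precision and missed differences.** SE = SD × √(1/n₁ + 1/n₂); half-width = t(0.975, df) × SE. The probability of P>0.05 at a true difference δ is the noncentral t probability between −t and +t, with noncentrality δ/SE. For example, at 38/31 and SD 3.3: SE = 3.3 × 0.2420 = 0.799; half-width = 1.996 × 0.799 = 1.59; noncentrality at 1.5 mmHg = 1.5/0.799 = 1.88.

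| n per arm | SD (mmHg) | SE | 95% half-width | Largest observed difference with 95% CI inside ±3 | P>0.05 if true difference is 1.5 mmHg |
|---|---|---|---|---|---|
| 38/31 | 3.3 | 0.80 | 1.59 | 1.41 | 54% |
| 38/31 | 4.35 | 1.05 | 2.10 | 0.90 | 71% |
| 27/25 | 3.3 | 0.92 | 1.84 | 1.16 | 64% |
| 27/25 | 4.35 | 1.21 | 2.43 | 0.57 | 77% |

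The 1.5 mmHg value (about half of 2.99) is an illustration, not a proposed margin.

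**5. What the table implies.** Between-group limits inside ±3 mmHg are attainable, so the interval sentence could be a true between-group statement. If the lasers were identical, simulation gives a chance of meeting ±3 mmHg at one interval of about 92% to 60% at 38/31 and 79% to 37% at 27/25, from the lower to the upper SD. P>0.05 on its own is weak evidence: in every row a 1.5 mmHg difference would be missed more often than found.

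**The case against.** The strongest reply is that the conclusion does not rest on P-values alone. If the intervals are between-group, five of the six tabulated intervals exclude a 3 mmHg difference, and no miss is reported on the percentage scale. The document also says comparable, not equivalent or non-inferior, prints its P-value basis in the same sentence, and names its own exception. Much of this stands. The interval sentence may be informative, and whether it is depends on figures not seen here. It does not turn the P>0.05 sentence into a demonstration, because the bound was never set as an acceptable between-laser difference.

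A reader might infer several stronger things that the documents do not support:

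- **That the 20.0% bound is a switch to a looser standard than 16.19%.** It is not: 3 mmHg or 20.0% is the prior-study pair that the opening section itself cites, and the Results use that same pair.
- **That week 24–36 contradicts the all-intervals claim.** That phrase belongs to the P-value sentence. The interval sentence is separate and carries its own exception.
- **That week 24–36 was removed or hidden, or failed on both scales.** Nothing says that data were dropped, and the miss is reported only for the absolute scale.
- **That the trial had little chance of meeting ±3 mmHg.** That follows only at the upper SD and the smaller n; at the lower SD the chance is about 92% to 79%.
- **That the lasers differ.** Nothing here shows that.

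**Conclusion.** The point holds as a matter of inference and reporting. The text supports a finding of no statistically significant difference. If the intervals are between-group, it also supports excluding differences of about 3 mmHg or 20.0% where the bound was met. It does not support comparability demonstrated at every interval.

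The size rests on an assumed SD of 3.3 to 4.35 mmHg, on a two-sided test, and on 38/31 or 27/25 patients. Differences of about 1.5 mmHg would probably have gone undetected across that whole range. The actual between-group interval cannot be computed from the text, and the percentage scale was not sized. The label on week 24–36 is a lesser matter of wording, since the miss itself is disclosed. The correction should be made, but no fault in the data is alleged.

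**What to change.** - Replace the claim of demonstrated comparable decreases with: *no statistically significant difference was detected; the trial was not designed to establish equivalence or non-inferiority*.
- Report the between-group mean difference with its 95% confidence interval and n per arm at each interval, on both scales, unless Figures 1 and 2 already do so.
- State in the text whether the quoted intervals are per-arm or between-group.
- Replace the outlier label with a plain statement that the week 24–36 interval did not lie within 3 mmHg on the absolute scale.
- Label any equivalence or non-inferiority analysis post hoc.

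The cost is one reworded paragraph and, if the figures lack them, a few intervals from existing data. No new data are needed. The drawback for the sponsor is a less favourable conclusion.
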